Date of Issue: 04 December 2019

Covance Study ID:000000155200

NIMP:	noninvestigational medicinal product
OAD:	oral antidiabetes drug
PCSA:	Potentially Clinically Significant Abnormality
PQAT:	Patient Qualitative Assessment of Treatment
PT:	preferred term
PTH:	Parathyroid hormone
SAE:	serious adverse events
SBP:	systolic blood pressure
SD:	standard deviation
SE:	standard error
SMBG:	self-monitored blood glucose, self-monitored blood glucose
SOC:	system organ class
TC:	total cholesterol
TEAE:	treatment-emergent adverse event
TG:	triglycerides
TRIM-D:	Treatment Related Impact Measure - Diabetes
UACR:	urinary albumin creatinine ratio, urinary albumin creatinine ratio
ULN:	upper limit of normal
WHO-DD:	World Health Organization-Drug Dictionary, World Health Organization-Drug Dictionary

1 OVERVIEW AND INVESTIGATIONAL PLAN

1.1 STUDY DESIGN AND RANDOMIZATION

This is a Phase 3, multicenter, randomized, double-blind (with single-blind Run-in Phase), placebo-controlled, parallel-group stratified study. Patients are to be randomly assigned 2: 1: 1 to the following 3 treatment groups

- Sotagliflozin 400 mg
- Sotagliflozin 200 mg
- Placebo

All patients will have Screening Period comprised of a Screening Phase of up to 2 weeks and a 4-week Lantus titration/single-blind placebo titration Run-in Phase prior to randomization.

Following randomization, patients will have a 52-week double-blind Treatment Period, and a 2-week post-treatment Follow-up period (patients who prematurely discontinue the study treatment are expected to continue in the study).

At the end of screening period, eligible patients are centrally randomized (using permuted block randomization schedule) via interactive response technology (IRT) in a 2:1:1 ratio to Sotagliflozin 400 mg group, Sotagliflozin 200 mg group and Placebo group. The randomization will be stratified by hemoglobin A1c (HbA1c) ($\leq 8.5\%$, $> 8.5\%$) and systolic blood pressure (SBP) (< 130 mmHg, ≥ 130 mmHg) and sulfonylureas use (Yes, No) at Week -1.

It is anticipated to randomize a total of approximately 560 patients (Sotagliflozin 400 mg: 280; Sotagliflozin 200 mg: 140; Placebo: 140).

Continuous Glucose Monitoring sub-study (CGM sub-study)

Approximately 132 eligible patients participating at a number of pre-selected sites in the United States will also be involved in the CGM sub-study with approximately 66 patients in the sotagliflozin 400 mg arm, 33 patients in the sotagliflozin 200 mg arm and 33 patients in the placebo arm. Two CGM assessment periods are planned: Baseline CGM during Week -1 for 7 consecutive days and post-randomization CGM during Week 18 and 19 for 14 consecutive days. Both patients and investigators will be masked to glucose values.

1.2 OBJECTIVES

1.2.1 Primary objectives

The primary objective of this study is to demonstrate the superiority of sotagliflozin 400 mg versus placebo with respect to HbA1c reduction at Week 18 in patients with type 2 diabetes mellitus (T2D) inadequate glycemic control on basal insulin alone or with OADs.

1.2.2 Secondary objectives

- To assess the effects of sotagliflozin 400 mg versus placebo on:
 - Change from Baseline to Week 18 in FPG
 - Change from Baseline to Week 18 in BW
 - Change from Baseline to Week 12 in SBP for patients with Baseline SBP \geq 130 mmHg
 - Change from Baseline to Week 12 in SBP for all patients
 - Change from Baseline to Week 52 in HbA1c
 - Change from Baseline to Week 52 in BW
- To assess the effects of sotagliflozin 200 mg versus placebo on:
 - Change from Baseline to Week 18 in HbA1c
 - Change from Baseline to Week 18 in BW
 - Change from Baseline to Week 18 in FPG.
 - Change from Baseline to Week 12 in SBP for patients with Baseline SBP \geq 130 mmHg
 - Change from Baseline to Week 52 in HbA1c
 - Change from Baseline to Week 52 in BW
- To evaluate the safety of sotagliflozin 400 mg and 200 mg versus placebo throughout the 52-week trial.

1.2.3 Other objectives

- To assess the effects of sotagliflozin 400 mg versus placebo on the proportion of patients with HbA1c $<$ 7% or HbA1c $<$ 6.5% at Weeks 18, 26, and 52
- To assess the effects of sotagliflozin 200 mg versus placebo on the proportion of patients with HbA1c $<$ 7% or HbA1c $<$ 6.5% at Weeks 18, 26, and 52
- To assess the effects of sotagliflozin 200 mg versus placebo on the change from Baseline to Week 12 in SBP for all patients
- To assess the effects of sotagliflozin 400 mg and 200 mg versus placebo on:
 - Change from baseline to Week 26 in HbA1c

- Change from Baseline to Weeks 26 and 52 in SBP in all patients and the subset of patients with Baseline SBP ≥ 130 mmHg
 - Change from Baseline to Weeks 12, 26, and 52 in SBP in patients with Baseline SBP < 130 mmHg
 - Change from Baseline to Weeks 12, 26, and 52 in diastolic blood pressure (DBP) for all patients and the subset of patients with Baseline DBP ≥ 80 mmHg
 - Change from Baseline to Week 52 in the total daily insulin dose
 - Proportion of patients requiring rescue therapy during the 52-week double-blind Treatment Period
 - Change from Baseline to Week 18 and Week 52 in 7-point Self-Monitored Blood Glucose (SMBG) profile (mean daily value at each time point)
 - Change from Baseline on estimated glomerular filtration rate (eGFR)
 - Change from Baseline in urinary albumin creatinine ratio (UACR)
 - Patient Qualitative Assessment of Treatment (PQAT) during the 52-week Treatment Period
 - Patient perception of treatment impact and satisfaction using the TRIM-D during the 52-week Treatment Period.
- To assess plasma concentrations of sotagliflozin and its 3-O-glucuronide metabolite.

1.2.4 Objectives of CGM sub-study

1.2.4.1 Primary sub-study objective

To compare the effect of sotagliflozin 400 mg versus placebo on the percentage of time within the glucose range of 70 to 180 mg/dL (3.9 to 10.0 mmol/L) over 24 hours, as assessed with CGM

1.2.4.2 Secondary sub-study objectives

- To compare the effect of sotagliflozin 200 mg versus placebo on the percentage of time spent within the glucose range of 70 to 180 mg/dL (3.9 to 10.0 mmol/L) over 24 hours, as assessed with CGM
- To compare the effect of sotagliflozin (200 and 400 mg) versus placebo over 24 hours, as assessed by CGM, on the following:
 - Mean 24 hour glucose concentration
 - Percentage of time spent within the glucose range of 70 to 140 mg/dL (3.9 to 7.8 mmol/L)
 - Coefficient of variability (CV) of glucose concentrations
 - AUC of glucose concentrations for 2 hours after a standardized mixed meal

- 2 hour postprandial plasma glucose (PPG) following a standardized mixed meal.

1.2.4.3 Other sub-study objectives

To compare the effects of sotagliflozin (200 and 400 mg) versus placebo on the following:

- Percentage of time over 24 hours with glucose levels >140 mg/dL (>7.8 mmol/L), >180 mg/dL (>10.0 mmol/L), >250 mg/dL (>13.8 mmol/L), <70 mg/dL (<3.9 mmol/L), and <54 mg/dL (<3.0 mmol/L)
- Percentage of time over 24 hours spent within the target range of 70 to 180 mg/dL (3.9 to 10.0 mmol/L) during the diurnal period (6:00 AM to 11:59 PM) and nocturnal period (0:00 AM to 5:59 AM)
- AUC of glucose concentrations over 24 hours >140 mg/dL (>7.8 mmol/L), >180 mg/dL (>10.0 mmol/L), >250 mg/dL (>13.8 mmol/L), <70 mg/dL (<3.9 mmol/L), and <54 mg/dL (<3.0 mmol/L)
- Various measures of glucose variability including Mean Amplitude of Glycemic Excursion (MAGE), standard deviation (SD) of glucose levels within and between days, and interquartile range (IQR)
- Proportion of patients (%) with at least one hypoglycemic episode defined as CGM values <70 mg/dL (<3.9 mmol/L) for ≥ 15 minutes.

1.3 DETERMINATION OF SAMPLE SIZE

The sample size/power calculations were performed based on the primary endpoint, change in HbA1c from baseline to Week 18 between sotagliflozin 400 mg and placebo. Assuming a common standard deviation (SD) of 1.2% and using a 2-sided test at a 0.05 α -level, 280 patients in the sotagliflozin 400 mg arm and 140 patients in the placebo arm will provide at least 95% power to detect a treatment difference of 0.5% in mean HbA1c change from Baseline to Week 18 between sotagliflozin 400 mg and placebo.

A sample size of 140 patients in the sotagliflozin 200 mg arm and 140 patients in the placebo arm will provide 80% power to detect a treatment difference of 0.4% in mean HbA1c change from Baseline to Week 18 between sotagliflozin 200 mg and placebo (SD 1.2%; 5% significance level 2-sided).

The total sample size will be 560 patients to be randomized (280 patients in the sotagliflozin 400 mg arm; 140 patients in the sotagliflozin 200 mg arm; 140 patients in the placebo arm).

The sample size/power calculations for the CGM sub-study are based on the primary variable, change from Baseline to Week 19 in the percentage of time within the target range of 70 to 180 mg/dL over 24 hours for sotagliflozin 400 mg as compared to placebo. Assuming a common standard deviation of 18%, a common missing rate of 15% and using a 2-sided test at a 0.05 α -level, 66 patients in the sotagliflozin 400 mg arm and 33 patients in the placebo arm will

Statistical Analysis Plan

Version: Final 2.0

Lexicon Pharmaceuticals Protocol No. EFC14868

Date of Issue: 04 December 2019

[figure not shown]
Covance Study ID:000000155200

provide at least 80% power to detect a difference of 12% of time within the target range of 70 to 180 mg/dL over 24 hours between sotagliflozin 400 mg and placebo

[figure not shown]
The total sample size for the CGM sub-study will be 132 patients (approximately 66 patients in sotagliflozin 400 mg arm, 33 patients in the sotagliflozin 200 mg arm, and 33 patients in the placebo arm).

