The CGM primary endpoint of change in percentage of time glucose levels within the target range of 70 to 180 mg/dL (3.9 to 10.0 mmol/L) over 24 hours from baseline to Week 19 will be analyzed by an ANCOVA model using the values measured at baseline and Week 19 (observed or imputed). The missing CGM values at endpoint will be imputed by multiple imputation (MI) methods as described below.

Note that the comparison of change in percentage of time glucose levels within the target range of 70 to 180 mg/dL (3.9 to 10.0 mmol/L) over 24 hours from baseline to Week 19 between sotagliflozin 200 mg and placebo is a CGM sub-study secondary endpoint, however the analysis is identical to that of CGM primary endpoint and is detailed here for concision.

Missing endpoint data at Week 19 visit will be imputed using a model built separately in each treatment group and estimated from the patients in the same treatment group who prematurely discontinue the IMP before the Week 19 visit but have the measurement for the endpoint (retrieved dropouts). The imputation model will include the randomization strata and the corresponding baseline value. In cases of non-convergence during the imputations, the offending stratum will be identified and then will be dropped from the model. Considering that the number of patients in each treatment group who discontinue the IMP but have the measurement for the endpoint is expected to be small, a simple imputation model based on regression will be used with baseline measurement included as the predictor. This will serve as the primary model of imputation for missing data should sampling criteria be satisfied (see below).

An alternative (back-up) imputation method will be used if the number of patients who prematurely discontinue the IMP before the Week 19 visit but have the measurement for the endpoint is <5 in any treatment groups (ie, not sufficient retrieved dropouts to support the imputation method described above). This criterion will be assessed for each CGM sub-study primary or continuous secondary endpoint.

In the back-up imputation method, missing post-baseline endpoint values at Week 19 will be imputed by washout multiple imputation (MI) method under the missing not at random (MNAR) framework.

Missing endpoint data at Week 19 in the sotagliflozin group(s), as well as in the placebo group are imputed from a model estimated from patients in the placebo group who have the endpoint data available.

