For patients in the sotagliflozin 400 mg and 200 mg groups with missing data at Week 19, their missing values will be imputed using observed baseline and the observed primary endpoint data from placebo completers; no intermittent values from either placebo or the active treatment groups will be used.

For placebo patients, missing data will be imputed based on the placebo group data. Intermittent observed values will be used while imputing missing values at Week 19. In cases that a non-monotone missing data pattern occurs at the intermediate visits, these data points will be first imputed in the placebo group using the Markov Chain Monte Carlo (MCMC) option in PROC MI to achieve a monotone missing pattern for all placebo patients. The Week 19 endpoint values will be subsequently imputed from the multiple copies of the original dataset where each copy will have a monotone missing pattern.

The imputation models for the washout MI method will include the randomization strata and the corresponding baseline value. Missing data will be imputed using the regression method. In cases of non-convergence during the imputations, especially for the MCMC application in the placebo non-monotone datasets, graphical measures (eg, trace and autocorrelation plots) will be used to identify the offending variable and once detected, that variable(s) will be dropped from the model and the imputations will be re-run. These re-run models will use the same seed number and number of imputations as used in the original models.

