	Scr	Run-in Lantus titration, single-blind placebo				No titration of Lantus (except for safety)								Lantus titration permitted			
VISIT	1	2	3☞	4☞	5	6	7☞	8	9☞	10	11	12A ^a	12 ^b	13	14	15	16
Week	-6	-4	-3	-2	-1	0	2	4	6	8	12	17	18	26	39	52	54
Day (window [days])	-42	-28 (±3)	-21 (±2)	-14 (±2)	-7 (±2)	1 (-)	14 (±3)	28 (±3)	42 (±3)	56 (±3)	84 (±3)	119 (±3)	126 (±3)	182 (±3)	273 (±7)	364 (±7)	378 (±3)
CGM sub-study procedures					Baseline CGM							Post-randomization CGM					
Informed consent	X																
Eligibility	X					X											
CGM Training/Review					X							X					
Dispense CGM supplies					X							X					
CGM sensor insertion					X	X ^c						X	X				
CGM start					X							X					
Mixed-Meal Tolerance Test ^d (MMTT)						X							X				
Collect CGM supplies						X							X				
Upload CGM data to PC and review the quality report						X							X				

- ^a Patients in the CGM sub-study will return to the study site for an additional visit (Visit 12A) at the end of Week 17 for insertion of CGM sensors for the post-randomization CGM assessment which will be conducted over Weeks 18 and 19. If a patient discontinued the IMP before Visit 12A, the post-randomization CGM and the MMTT will not be performed.
- ^b For patients in the CGM sub-study, at Visit 12 the CGM sensors will be replaced for continuing the next 7-day CGM. For patients in the CGM sub-study, during Week 19 the total Lantus dose should remain stable (dose change less than ±10%, or less than ±4 Units, whichever is less). At the end of Week 19 patients will remove the CGM sensor at home and return the device and supplies (including sensor, transmitter, and receiver) to the study site in person or via mail using the provided packaging. Following removal of the CGM sensor, Lantus titration may resume as needed.

Statistical Analysis Plan

Version: Final 2.0

Lexicon Pharmaceuticals Protocol No. EFC14868

Date of Issue: 04 December 2019

Covance Study ID:000000155200

- c Repeat 7-day CGM assessment conducted ONLY for patients who fail to provide adequately usable CGM data during the previous 7 days. In such a case, randomization will be postponed for 7 days and MMTT will be repeated.
- d Mixed meal tolerance test is to be performed while CGM sensor is in place and functioning.

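### The CGM sub-study power of 80% or more treats the 15% missing as lost sample size, but the analysis that will almost certainly apply gives them placebo-based values; on the SAP's own inputs power is then about 70%

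*SAP*

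**What the plan says.** SAP 1.3 sizes the CGM sub-study on the change from Baseline to Week 19 in percentage of time at 70 to 180 mg/dL, 400 mg against placebo. The inputs are a "common standard deviation of 18" percent, "a common missing rate of 15" percent, a test "using a 2-sided test at a 0.05" level, and "66 patients in the sotagliflozin 400 mg arm and 33 patients in the placebo arm". On these the SAP claims to "provide at least 80% power to detect a difference of 12% of time within the target range".

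SAP 2.4.4.5 describes the analysis. Missing Week 19 values are first imputed within each arm from patients who "prematurely discontinue the IMP before the Week 19 visit but have the measurement for the endpoint (retrieved dropouts"). If any arm has fewer than five such patients, a back-up washout method replaces this. Under washout, for sotagliflozin patients with missing data, "their missing values will be imputed using observed baseline and the observed primary endpoint data from placebo completers". Each completed dataset goes into an ANCOVA and the results are combined.

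The CGM sub-study flow chart in SAP Appendix D adds, in footnote a: "If a patient discontinued the IMP before Visit 12A, the post-randomization CGM and the MMTT will not be performed". Visit 12A is at Week 17 (Day 119).

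**The concern.** A missing rate can enter a power calculation in two ways. If the missing patients are left out, sample size falls and the treatment effect is untouched. If missing patients on active treatment receive values drawn from a placebo model, they remain in the analysis but contribute no expected treatment difference, so the effect shrinks as well. SAP 1.3 appears to use the first approach, while SAP 2.4.4.5 is very likely to lead to the second.

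Under washout this applies to every missing sotagliflozin value, whatever the reason, including a patient still on treatment who has too few usable CGM days.

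At stake is the stated sensitivity of the sub-study's primary comparison. A reader who takes 80% or more at face value would read a non-significant result as stronger evidence against a 12-point effect than the prescribed analysis can give.

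**Working it through.** **Inputs (SAP 1.3).** Difference 12 points, SD 18, two-sided 0.05, 66 v 33 enrolled, 15% missing in each arm.

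**Step 1: reproduce the stated power.** Removing 15% leaves 0.85 × 66 = 56.1 and 0.85 × 33 = 28.05.
- SE = 18 × √(1/56.1 + 1/28.05) = 4.16.
- Power = Φ(12/4.16 − 1.96) = 82.2%, or 81.3% with the noncentral t. At whole numbers, 56 v 28, the t version gives 81.2%.
- With 2:1 allocation, 27 evaluable placebo patients give 79.8% and 28 give 81.2%. Then 28/0.85 = 32.9, which rounds up to the stated 33.
- With no missing data (66 v 33), SE = 3.84 and power is 87.8% (z) or 87.2% (t).

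The stated size and power therefore match missing patients treated as lost sample size, with the full 12 points kept.

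**Step 2: which imputation will apply.** By footnote a, a retrieved dropout in the sub-study must stop study drug between Visit 12A (Day 119) and Week 19, a span of about two weeks. SAP 2.4.4.5 also requires at least 4 usable days of CGM. Avoiding washout needs five such patients in every arm. In each arm of 33 that is 5/33, about 15% of the arm, stopping inside that span. This is not impossible, but it is not a realistic planning case.

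**Step 3: effect under washout.** Imputed sotagliflozin patients have an expected difference from placebo of zero, so the expected estimate is 0.85 × 12 + 0.15 × 0 = 10.2 points.

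**Step 4: power under washout.**
- SE at the evaluable sample size: Φ(10.2/4.16 − 1.96) = 68.8% (z), 67.8% (t).
- SE at the full sample size, which credits imputed values as real data and so bounds power from above: Φ(10.2/3.84 − 1.96) = 75.7% (z), 74.9% (t).
- Simulation of placebo-based multiple imputation with ANCOVA and Rubin's rules (3000 trials, 50 imputations): 69% to 70%. Repeat runs of 3000 to 6000 trials with other numbers of imputations gave 68% to 70% and a mean estimate of 10.2 to 10.3.
- At a true difference of 13.5 points, simulated power is 79% to 80%. The expected estimate is then 0.85 × 13.5 = 11.5.

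Two simplifications apply. The simulated ANCOVA adjusts for baseline but not for strata, injection time or country. Rubin's rules are named for the main primary endpoint in SAP 2.4.4.1 and assumed here, since 2.4.4.5 says only that results are combined.

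**Step 5: other missing rates** (normal approximation, true difference 12, SD 18).

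| Missing | Patients removed, full 12 points | Diluted effect, full-n SE (upper bound) | Diluted effect, evaluable-n SE |
|---|---|---|---|
| 5% | 86.2% | 84.4% | 82.5% |
| 10% | 84.3% | 80.4% | 76.1% |
| 15% | 82.2% | 75.7% | 68.8% |
| 20% | 79.9% | 70.6% | 60.9% |

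**Step 6: other readings of the inputs, at 15% missing.**
- If 12 points is the overall difference after placebo-based imputation, the difference among observed patients is 12/0.85 = 14.1 points, and power is about 82% to 84%.
- If 18 is an unadjusted SD and baseline correlates 0.3 with change, simulated power is about 73% under washout against 84% to 86% with missing patients removed. At a correlation of 0.5 the figures are about 82% and 91%. Across correlations of 0, 0.3 and 0.5, washout costs about 9 to 13 percentage points.

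**The case against.** The strongest reply is that SAP 1.3 does not say what 12 and 18 refer to. The sub-study population is drawn from the ITT population, and values after discontinuation count, so 12 points could be meant as the overall difference under that strategy; it would then not be diluted again. Likewise 18 could be an unadjusted SD, with the ANCOVA recovering precision. The protocol refers CGM statistics to a separate sub-study protocol, which may give the basis. This stands: 70% is conditional, and on some readings the claim of 80% survives. The same reply, though, shows that SAP 1.3 leaves its own figure undetermined.

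A second reply is that washout is only the back-up. That is true on paper. A reader might infer from footnote a that the retrieved-dropout step can never operate. The documents do not support that, because a stop between Visit 12A and Week 19 can qualify. The prespecified switch at fewer than five already covers the likely case.

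A third reply is that the sub-study lies outside the main fixed-sequence family, and that the reported 95% confidence interval will show the precision achieved. Both are true. They limit the consequence but do not make the planning statement match the analysis.

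**Conclusion.** The claim of 80% or more does not correspond to the analysis that SAP 2.4.4.5 will almost certainly deliver. Taking 12 points as the difference among observed patients and 18 as the residual SD, which is how the SAP's own calculation uses them, power is about 70% and at most about 75%. The shortfall disappears only if 12 is already the diluted difference, or if 18 is unadjusted and the baseline correlation is near 0.5.

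Two stronger readings are tempting. A reader might infer that the sample size arithmetic is wrong; it is not, since it reproduces exactly under its own premise, and the fault is a mismatch between planning assumption and analysis method. A reader might also infer that the imputation method is defective or that the sub-study is simply a 70% study; the documents establish neither. The main trial's primary comparison is unaffected.

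**What to change.** In SAP 1.3, restate the CGM power under washout imputation: about 70% for a 12-point difference with 15% missing, or give the roughly 13.5-point difference that has 80% power. In the same paragraph, state whether 12 points is before or after placebo-based imputation and whether 18 is the residual SD after baseline adjustment. If the sponsor intended either of the more favourable readings, saying so, with the implied difference among observed patients or the assumed baseline correlation, would settle the point.

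No change to the imputation rule in SAP 2.4.4.5 is needed. The cost is SAP wording and, on the SAP's own inputs, a less favourable stated power; no extra patients and no change to conduct or analysis.
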